5.1.8 Achieving SEF target

The EEG SEF targets will be different for each of the three stimuli (e.g., the propofol dose and anesthetic depth to block response to placement of oral pacifier is less than for electrical stimulation and laryngoscopy). Based on our clinical experience, the initial SEF targets for the first patient will be 20, 14, and 10hz for placement of oral pacifier, electrical stimulation, and laryngoscopy, respectively. For the same stimulus, the subsequent patient's target SEF will be determined by the previous patient's response to that stimulus, as

described in the section *Dixon up-down technique*. After sevoflurane washout (if applicable) and the propofol infusion dose and SEF are constant for 5 minutes, to ensure equilibration between propofol brain Ce and plasma concentration, the stimulus will be applied as described in the section *EEG vs Propofol Ce*. If current SEF is higher than target SEF, additional propofol (0.5-2mg/kg boluses and/or 10-20% increases in propofol infusion rate) can be given to decrease SEF closer to target SEF. Conversely, if current SEF is lower than target SEF, propofol infusion rate can be decreased 10-20% or temporarily paused to increase SEF to target SEF.

5.2 Laboratory test

Blood samples will be sent to Institutional Core laboratory at CHOP for batch processing to measure plasma propofol concentration.

5.3 Safety Evaluation

Patient safety will be monitored by adverse events, vital signs, and patients' response.

5.4 Non-evaluable Subjects

Non-evaluable subjects include 1) patient received IV medication other than propofol and midazolam from the anesthesia team during study phase, 2) unable to get EEG SEF reading during study phase, or 3) unable to decrease expired sevoflurane to $\leq 0.2\%$ during study period.

6 STATISTICAL CONSIDERATIONS

6.1 Primary Endpoint

Three EEG SEF₅₀ values corresponding to where 50% of patients do not respond to 1) placement of oral pacifier EEG SEF₅₀, 2) electrical stimulation EEG SEF₅₀, and 3) laryngoscopy EEG SEF₅₀.

6.2 Secondary Endpoints

The propofol effect site concentration corresponding to each EEG SEF₅₀ will be determined from the regression between plasma propofol concentration vs SEF recorded at the time of the blood draw.

6.3 Statistical Methods

[figure not shown]
6.3.1 Baseline Data

Baseline and demographic characteristics will be summarized with standard descriptive summaries (e.g. means and standard deviations for continuous variables such as age and percentages for categorical variables such as gender).

6.3.2 EEG SEF

[figure not shown]
The median EEG SEF (SEF_{50}) for a stimulus is the SEF where half the patients do not respond to that particular stimulus. SEF_{50} will be determined for each of the three stimuli for the 3-12 mo and 13-24 mo age groups. For each stimuli, each SEF crossover pair (Yes to No response or vice versa) in the *Dixon's up-down* response will be treated as a SEF pair and the mean SEF_{50} and standard deviation of the SEF pairs will be determined. See figure below for example of Dixon's up-down method and determination of SEF_{50} for laryngoscopy. X axis represents sequential patients #1 to #30, Y axis represent SEF levels. Each blue (Yes response) and red (No response) dot represent a patient. The orange bars on the X axis represent crossover pairs, used to calculate SEF_{50} .

In the laryngoscopy example below, the mean SEF_{50} is 8.22hz and standard deviation is 1.83hz, derived from crossover points: 5, 9, 9, 9, 9, 9, 7, 7, 5, 7, 7, 7, 7, 11, 11, 11, 9, 9hz.

6.3.3 Propofol Ce

The propofol plasma concentration will be determined by laboratory measurements. A regression curve will be determined from the plot of plasma propofol concentration vs SEF at the time the blood was drawn for the propofol level. At steady state, plasma propofol and propofol Ce are equal. The propofol Ce corresponding to each SEF_{50} will be calculated from the regression. There will be two regression curves, one for the 3-12 mo age group and the other for the 13-24 mo age group. See figure below for example of Propofol Ce vs SEF curve for one age group; x-axis is SEF and y-axis is propofol Ce.

6.3.4 Sample Size and Power

Many anesthesia studies utilizing the Dixon up-down design have a sample size of 10-30 for each stimulus.²³ Hammer et al. used the *Dixon up-down* method to determine the propofol median effective dose (ED50) to prevent movement in children undergoing gastro-endoscope insertion with a sample size of 12.³¹ Endoscope insertion is a procedure similar to laryngoscopy. We propose a sample size of 30 for each stimulus for each age group.

Because only one or two stimuli can be performed per patient within the proposed study time (e.g., placement of oral pacifier before laryngoscopy, or nerve stimulation before laryngoscopy), the required sample size of subjects for each age group needs to be up to 60, for a total of 120 evaluable patients. Two age groups are selected because of normal age-dependent EEG changes in the first few years of life that could affect the EEG SEF.

6.4 Safety Analysis

During the study period, adverse events (AE) are defined as:

- 1- Oxygen desaturation (< 85% for more than 30 seconds).
- 2- Hypotension (mean arterial pressure < 40 mmHg for 3-12 mo and < 45 mmHg for 13-24 mo across at least two measurements).
- 3- Bradycardia (HR < 60 bpm for more than 30 seconds) will be recorded for all patients.
- 4- Overhead call for emergency help.
- 5- Laryngospasm requiring intervention.

AE incidence will be summarized along with the corresponding SEF values during the occurrence.

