Sequential allocation trial using *Dixon's* up-down technique. To achieve the EEG SEF target, initial propofol dosing will be based on a published age-based dosing table used clinically at CHOP. The EEG SEF target for a specific stimulus will be determined by the previous patient's response to that same stimulus. If the previous patient responded to the stimulus, then the current patient will have a lower SEF target for the same stimulus. Conversely, if the previous patient did not respond to the stimulus, then the current patient will have a higher SEF target for the same stimulus. In the same patient, propofol dose adjustments may be needed between stimuli to achieve different SEF targets. The patient response to stimulus and EEG SEF will be recorded, along with a 1ml blood sample to determine propofol plasma level at a later date in the pharmacodynamic laboratory. The study will only be performed by the investigators listed in the study.

Patient Population**key criteria for Inclusion and Exclusion:****Inclusion Criteria**

- 1) Children 3 to 24 month old undergoing a procedure
- 2) Planned laryngoscopy and endotracheal intubation or LMA placement for clinical care
- 3) Planned propofol anesthesia for anesthesia maintenance.
- 4) ASA < III.
- 5) Muscle relaxant not indicated per planned clinical care for laryngoscopy/intubation.
- 6) Anticipated procedure duration approximately < 2h40min

Exclusion Criteria

- 1) Patients undergoing an emergency procedure
- 2) Known severe neurological disease which might result in abnormal EEG SEF.
- 3) Deformities of forehead (difficult EEG sensor placement).
- 4) Known difficult airway.
- 5) Allergy to propofol.

	
6) Attending anesthesiologist on record caring for patient plans to administer additional IV medication besides propofol during study phase.
 
7) Currently on anti-seizure medication (might alter propofol pharmacodynamics).

Number Of Patients	Up to 150 enrolled patients to produce 120 evaluable patients.
Study Duration	Each patient's participation will last from start of anesthesia to the last study stimulus.
Study Phases	From placement of second intravenous (IV) line or bolus of propofol (if IV is already present prior to induction) to the end of the last stimulus performed. Eligibility screening via reviewing procedure schedule and obtaining informed consent.
Screening	
Study	

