1.2 Relevant Literature and Data

Propofol Anesthesia

Propofol is FDA-approved for “Induction of General Anesthesia Patients ≥ 3 years of age and Maintenance of General Anesthesia Patients ≥ 2 months of age”.¹⁶ Propofol use in the study does not involve a route of administration, dose, patient population, or other factor that significantly increases the risk (or decreases the acceptability of the risk) associated with the use.

Propofol anesthesia consist of propofol bolus and infusion, which can be combined with regional anesthetic, opioids, dexmedetomidine, and/or muscle relaxant. For this study, only propofol will be administered during the study period which lasts from placement of the second IV or first propofol dosing until the end of the last stimulus. In patients with sevoflurane induction, sevoflurane will be washed out (patient expires the gas through breathing) prior to assessing EEG SEF and starting the first stimulation. Sevoflurane washout typically takes 5 minutes. After the study period (end of last stimulus), the anesthetic team on record caring for the patient can administer other medications as planned for the procedure.

EEG Monitor

The Masimo SedLine is a non-invasive 4-channel EEG monitor that is portable, easy and fast to apply to the forehead, and displays processed EEG. It is FDA-approved for use with adults and is widely used in both the adult and pediatric surgical population. We are interested in using the Spectral Edge Frequency (SEF)—a non-proprietary EEG parameter, to assess anesthetic depth. The Masimo Sedline’s

usability and safety profile has been established through our studies (17-014608 and 19-016071). The safety and efficacy of EEG SEF is not being evaluated as part of this study.

EEG Parameters vs Anesthetic Dose

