3.1.2 Study Interventional Phase

The study interventional phase will occur during the intraoperative period from after placement of second IV line or bolus of propofol (if IV line is present prior to induction) to the last stimulus.

EEG Monitoring

EEG monitoring will start after induction and end after the last stimulus.

Stimuli

At steady-state EEG SEF, two research stimuli (placement of oral pacifier and electrical stimulation) will be performed by the study investigator(s). The third stimulus, laryngoscopy—a clinically required procedure, will be performed by the anesthesia team on record caring for the patient.

Propofol dosing

Adjustment to propofol infusion and dosing is considered standard of care and is needed to achieve different anesthetic depths and SEF targets for different stimuli. As described in the study flowchart below, if current SEF is below target SEF, then propofol dose will be decreased. Conversely, if current SEF is above target SEF, then propofol dose will be increased.

Second IV Placement

An IV separate from the propofol infusion line will be placed in order to draw blood samples to evaluate propofol plasma concentration. Often the second IV will also be clinically indicated regardless of study status. If the second IV line is unable to be placed, a butterfly needle may be used to draw a single sample.

Blood Sample Collection

Up to three 1ml blood samples, for a total of 3ml, will be collected during the study interventional phase.

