5.1.4 Stimuli

For this study, laryngoscopy is clinically required for anesthesia and the procedure, whereas electrical stimulation are often performed, but may not always be clinically required.

Depending on time constraints, each patient may have two to three stimuli applied in sequence (placement of oral pacifier, electrical stimulus, and laryngoscopy). Based on responses to each stimulus, the SEF target and propofol dose may be adjusted for the next

stimulus. Each stimulus may only be applied once per patient and all stimuli will be completed prior to intubation.

If sevoflurane was used during anesthesia induction, then sevoflurane will need to be washed out prior to performing the first stimuli, to avoid residual sevoflurane's effects on the brain and EEG. This can be done by turning off sevoflurane to allow the patient to expire the sevoflurane through breathing. Sevoflurane washout is complete when end tidal sevoflurane concentration < 0.2%. Propofol infusion and EEG monitoring will start prior to completing sevoflurane washout.

Placement of oral pacifier

After anesthesia induction, sevoflurane washout (if applicable), and EEG SEF at the target for placement of oral pacifier, an oral pacifier will be placed in the patient's mouth. The oral pacifier will be withdrawn if there is a positive response (defined in section 5.1.5) or when 5 seconds has elapsed.

Electrical stimulus

The study team will assess forearm skin integrity prior to applying the nerve stimulator electrodes. After sevoflurane washout (if applicable) and EEG SEF at the target for electrical stimulus, a nerve stimulator (Halyard EZstim, Halyard Health Inc) will be initiated at 50hz 30mA for up to 15 seconds.³⁰ The electrical stimulus will stop if there is a positive response (defined below) or when 15 seconds has elapsed.

Laryngoscopy

After sevoflurane washout (if applicable) and EEG SEF at the target for laryngoscopy, laryngoscopy will be performed by the anesthesia team on record caring for the patient. This will mark the end of the stimuli interventions. If no response to laryngoscopy is elicited, the anesthesia team on record may choose to intubate the patient or administer additional medications. If a positive response to laryngoscopy is elicited, the anesthesia team on record may choose to stop laryngoscopy and/or administer additional medications such as neuromuscular relaxant.

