Responses to the stimuli will be recorded. The patient will be monitored closely by the study team for any adverse events. Study interventions will occur simultaneously with routine clinical anesthesia and surgical care; therefore, there will be no additional time under anesthesia from this study. Not every patient will have all three stimuli performed and some patients may have only one research stimuli performed. Study procedures will be stopped once all standard, clinical care preparation for surgery is completed.

The same stimulus will not be applied twice to the same patient. The patient's study involvement will conclude once laryngoscopy has been performed on the patient and blood

draw (if applicable) has been performed. The remainder of the anesthetic will be per routine care.

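### The adverse-event count in section 6.4 closes at the last stimulus, so events that begin just after a laryngoscopy at a study-assigned SEF fall outside the only planned incidence and SEF summary

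*Protocol*

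**What the plan says.** Protocol section 6.4 lists five events: desaturation, hypotension, bradycardia, an overhead emergency call, and laryngospasm needing intervention. It opens with the window, "During the study period, adverse events (AE) are defined as", and closes with the planned analysis: "AE incidence will be summarized along with the corresponding SEF values during the occurrence".

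The window is defined elsewhere in the protocol:

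- Section 1.2 (Propofol Anesthesia) refers to the "study period which lasts from placement of the second IV or first propofol dosing until the end of the last stimulus".
- The synopsis agrees: "Each patient's participation will last from start of anesthesia to the last study stimulus".
- Section 3.1.2 runs the interventional phase from the second IV line or "bolus of propofol (if IV line is present prior to induction) to the last stimulus".
- Section 5.1.4 says of laryngoscopy, "This will mark the end of the stimuli interventions", and adds: "The patient's study involvement will conclude once laryngoscopy has been performed on the patient". That sentence goes on to include a blood draw where there is one.

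Section 8.3.1 ties the investigators' monitoring of each child to the same study period. Study EEG stops at laryngoscopy (section 5.1.2) or just after the last stimulus (sections 3.1.2 and 4.2.1). The SAP contains no safety analysis.

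**The concern.** Laryngoscopy is clinical care and would happen without the study. The depth at which it is done is different: sections 5.1.7 and 5.1.8 set the target SEF, starting at 10 Hz and then moving it by the previous child's response. The up-down rule holds that target near the level where about half the children respond. Section 8.3.2 names vocal cord closure and arterial desaturation among the risks of this step, and notes that these children receive no muscle relaxant for it.

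Section 6.4 sets out to report adverse events together with SEF. For the most stimulating of the three stimuli, its count stops as the exposure ends. An event provoked by laryngoscopy can begin, or first meet its criterion, after the blade is out. At stake is the completeness of the safety summary at laryngoscopy depth. The primary estimate does not depend on it.

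**Working it through.** The documents state no adverse-event rate, safety sample size or safety power, so there is no plan figure to reproduce. The check traces the window and then works out the weight of one omitted event.

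**1. Where the window ends.** Section 6.4 counts within the study period. Section 1.2 ends that period with the last stimulus, and section 5.1.4 makes laryngoscopy the last one when it is done. For a child with a study laryngoscopy, the 6.4 count therefore closes when laryngoscopy ends.

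**2. What is inside and outside.**

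- Inside: hypotension during titration, and laryngospasm or desaturation that meets its criterion before or during laryngoscopy.
- Outside: any of the five events that begins after laryngoscopy ends.
- Undetermined: desaturation and bradycardia must each last more than 30 seconds, and hypotension needs at least two measurements. Section 6.4 does not say whether onset or completion must fall in the window. If completion governs, a desaturation or bradycardia that starts in the last 30 seconds of laryngoscopy is also left out.

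**3. Whether other text extends the count.**

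- Section 3.2.1 describes study duration as the intraoperative period, but section 6.4 uses the term that section 1.2 defines.
- Section 4.3 records events after completion only if they are serious and related.
- Section 7.1 monitors events throughout the study and gives no later end point.
- Section 7.2 has events that need no prompt report summarized or tracked.
- Section 7.3 puts events on the case report form, but its definition names only children who had the pacifier or the electrical stimulus.

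Some of these may record a late event. None adds it to the 6.4 incidence, and no study SEF is planned for it because EEG has ended.

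**4. Weight of one omitted event.** With n children having a laryngoscopy in an age group, k omitted events lower the reported incidence by k/n. Section 6.3.4 gives the inputs: "We propose a sample size of 30 for each stimulus for each age group", with up to 60 evaluable children per age group. Both of its examples pair a research stimulus with laryngoscopy, so n may lie anywhere from 30 to 60.

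- n = 30, k = 1: 1/30 = 3.3 percentage points.
- n = 60, k = 1: 1/60 = 1.7 percentage points. The same holds if the denominator is all 60 evaluable children in the age group, or 30 laryngoscopies in each of the two groups pooled.
- All 120 evaluable children pooled, k = 1: 1/120 = 0.8 percentage points.

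The value of k cannot be obtained from the documents.

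**The case against.** The cut-off is a coherent choice. The study period is the propofol-only period. Once it ends, the anesthesia team may intubate, place an LMA, or give other drugs including a muscle relaxant, so later events are confounded. Study EEG has also stopped, so an SEF at the time of the event is not planned. Laryngoscopy complications can arise during the procedure, where they are counted, and later events have other routes to the record, with a DSMB reviewing safety. There is no safety hypothesis, comparison or stopping rule tied to section 6.4. That one event weighs 1/n is true of any omitted event.

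Much of this stands. It is why later events should be reported separately, carry a drug flag, and use an SEF from before laryngoscopy. It does not show that the 6.4 count is complete, since none of the other routes feeds that count.

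A reader might infer three stronger things that the documents do not support:

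- **That late events are lost to the study.** Sections 4.3, 7.2 and 7.3 may capture some, and the anesthetic records listed in section 5.1.1 may show others.
- **That incidence at individual SEF levels is distorted by a stated amount.** Section 6.4 plans incidence plus the SEF at each event. It plans no rate per SEF level and gives no per-level denominators, so no such figure can be claimed.
- **That because about half the children respond, about half are at risk of a counted event.** Under section 5.1.5 a response includes swallowing, sucking or facial movement, so the response rate says little about the rate of the five events.

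**Conclusion.** The point holds as a gap in the safety summary. Followed exactly, section 6.4 leaves out events that begin after a laryngoscopy done at a study-assigned SEF, and it does not say whether onset or completion decides. The number omitted is unknown and could be zero. The size given per event, 3.3 points at 30 laryngoscopies in an age group and 1.7 at 60, assumes that the incidence denominator is the children with a laryngoscopy (or all evaluable children, for the 1.7); section 6.4 does not name its denominator. SEF50 is unaffected. This is a cheap improvement to the plan, and the documents do not show that the omission is material.

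**What to change.** In section 6.4, for children who have a study laryngoscopy:

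- Count events with onset up to a short fixed time after the airway is placed, or after laryngoscopy ends if no airway is placed. Five minutes is an example; the documents give no length and the team should set it.
- State that onset inside the window governs, including for the criteria that need a minimum duration or repeat measurements.
- Report post-laryngoscopy events separately, with that child's laryngoscopy target SEF or the last SEF before laryngoscopy. Keep SEF at occurrence for earlier events.
- Flag any non-study drug given before the event.

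Keep the present end of the window for children with no study laryngoscopy. For children already studied (the SAP timeline has recruitment ending in June 2024), recover the added window from the anesthetic records in section 5.1.1 where they store readings often enough; the interval is not given. As an optional wording change, section 7.3 could name laryngoscopy at target SEF, and section 8.3.2 could say that its depth is set by the study.

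The cost is a few more minutes of adverse-event recording per child on monitors already in place, with no extra patients, procedures or anesthesia time. The downside is that some later events will reflect intubation or non-study drugs, which separate reporting and the flag make visible but do not remove.

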7 SAFETY MANAGEMENT

7.1 Clinical Adverse Events

Clinical adverse events (AEs) will be monitored throughout the study.

7.2 Adverse Event Reporting

Unanticipated problems related to the research involving risks to patients or others that occur during the course of this study (including SAEs) will be reported to the IRB in accordance with CHOP IRB SOP 408: Unanticipated Problems Involving Risks to Patients. AEs that do not meet prompt reporting requirements will be summarized in narrative or other format and submitted to the IRB at the time of continuing review (if continuing reviews are required), or will be tracked and documented internally by the study team but not submitted to the IRB (if continuing reviews are not required).

